At present, maintenance hemodialysis (MHD), globally, is the most common method of renal replacement treatment (RRT) for patients with end-stage renal diseases (ESRD). As a core technical problem of MHD, functional vascular access is the base of proceeding the treatment. It is well accepted as an important acknowledgment that native arterovenous fistulas (AVF) should be the first choice for vascular access. The construction of a functional AVF can be challenging, and high initial failure rates have been reported in many publications. Estimates of non-maturation rates vary from 10% to 33% in AVF. However, there are no well-established criteria that define fistula maturation. According to the vascular access guidelines of the National Kidney Foundation Kidney Disease Outcomes Quality Initiative (NKF-KDOQI), mature permanent access has a flow of approximately 600 mL/min and a minimum diameter of 0.6 cm and is less than 0.6 cm below the surface of the skin. The arterialized veins of AVF should have a flow of more than 500 mL/min and a diameter larger than 0.5 cm, and be less than 0.6 cm deep according to the Chinese Expert Consensus of Vascular Accesses for Hemodialysis. Even when the Chinese standard was considered, there were 31.2% (101/324 patients) non-mature AVF in stable long-term (more than six months) MHD patients in eight hemodialysis centers in our previous cross-sectional study. However, their AVF could support enough flow to get an effective urine clearance ratio ($Kt/V > 1.2$) during every hemodialysis session, which should be regarded as the functional accesses in our opinion. What are the differences between functional but non-mature AVF and function-and-maturation AVF? To the best of our knowledge, rarely there are reports on the functional access. Thus, in order to identify the characteristics of functional access in newly set-up AVF in MHD patients, we designed the prospective cohort study.

2. Aim of the study

To describe the ultrasound characteristics of newly set-up arteriovenous fistulas (AVF), also to identify predictors for maturation of AVF in the forearm.

To test the benefits of the ultrasound following-up protocol on AVF in MHD patients.

3. Methods

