3.1 Patients

Patients beginning MHD treatment in Peking University International Hospital from July 2016 will be screened. If patients fit to the selection criteria, they might be enrolled into the present study. Enrolled patients were divided into intervention group and control group.

3.1.1 Entry criteria:

- ① Regular hemodialysis patients (4 hours per session and three times a week).
- ② Planning to construct a new radiocephalic AVF in forearm.
- ③ 18-70 years old.

3.1.2 Exclusion criteria:

- ① Predicted duration of MHD less than six months, such as transferring to peritoneal dialysis, planning to kidney transplantation, or short life expectancy, etc.
- ② Have the following complications: malignant tumors, active rheumatism, malnutrition and cachexia.
- ④ Acute renal dysfunction.
- ④ Having done any blood vessel operations on the same side of the arms that planned to create an AVF. But it was not been care in the present study whether there were vascular accesses or not in the contralateral arm.
- ⑤ Not accepted AVF personally.
- ⑥ Other kinds of vascular accesses, such as brachiocephalic AVF, upper limb AVF, graft accesses, and so on.

3.2 Detection and following up of the intervention group:

The basic information of the patients, including gender, age, dialysis length, hemodialysis access, and primary causes of renal failure, will be collected. The baseline data will be recorded, including height, weight, BMI, and blood pressure (BP). Ultrasonography detection on the forearm blood vessels would be conducted before the surgery of AVF creation (time 0, t0). The operations will be conducted by a certain nephrologist with more than ten years experience of doing AVF surgeries. Until the patients finish the AVF operation, they would be followed up at least six months.

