3.3 Statistical analysis

Metrological data is expressed as mean \pm standard deviation (SD). The baseline variables are compared by independent t-test for measurement data and by χ^2 test for count data between Group M and Group N. The means of Kt/V are calculated for every patient and they are compared between two groups. Whether the AVF could be mature or not, predict factors are detected by Logistic Regression among these parameters on basement. The differences of the parameters between two groups are compared using General Linear Model Repeated Measures (GLM-RM) for continuous variables during following up. The results of GLM-RM can also identify the parameters' changes along with the timeline. The outcome events were compared between intervention group and control group. $P < 0.05$ is considered to indicate a significant difference. All of the analyses are performed using SPSS software (version 13.0 for Windows; SPSS Inc., Chicago, IL, USA).

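### Aim 2 (benefit of ultrasound follow-up) rests on one crude comparison: no primary event or time point, no stated allocation or adjustment, and scans described only for the intervention group

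*Combined protocol and SAP*

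**What the plan says.** Section 2 lists among the aims: "To test the benefits of the ultrasound following-up protocol on AVF in MHD patients". The background gives the design as "we designed the prospective cohort study". Section 3.1 describes how the groups arise only as "Enrolled patients were divided into intervention group and control group", with no method or ratio.

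The follow-up procedures in section 3.2 (baseline data, preoperative ultrasound, scans at two weeks and at two, three and six months, at least six months of follow-up) stand under the heading "Detection and following up of the intervention group". No section describes the controls' procedures. Section 3.2 ends with a list of access adverse events, to be recorded in enrolled patients. It names repeat surgery, thrombosis, stenosis, failed puncture and bleeding after dialysis, and is left open at the end.

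In section 3.3 the analysis for Aim 2 is "The outcome events were compared between intervention group and control group", followed by a general 0.05 significance threshold. The sentence beginning "The baseline variables are compared by independent t-test for measurement data" concerns Group M against Group N, not intervention against control.

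**The concern.** Three gaps affect the same comparison.

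- **Choice of event.** With several events listed and none made primary, the event and the time window can be chosen after the data are seen.
- **Who is in which group.** If allocation was not random, the groups may differ in prognosis. A crude comparison can then show a difference that is not due to the follow-up protocol, or hide one that is.
- **Unequal detection.** Ultrasound can find stenosis that would otherwise go unnoticed, and a scan finding can prompt an operation. If controls are scanned less often, both counts rise in the intervention group because of the scanning itself. A useful protocol could then look useless or harmful.

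At stake is whether the study can answer one of its stated aims. The work on maturation (Group M against Group N) is not affected by this point.

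**Working it through.** The documents give no sample size, event rate or effect size for intervention against control, so there is no planned figure to reproduce. The first step is a reading of the text. The others are illustrations on assumed inputs and show direction and rough size only.

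**1. What section 3.3 assigns to which comparison**

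| Element | Group M vs N, or maturation | Intervention vs control |
|---|---|---|
| Baseline comparison | t-test, chi-square | none stated |
| Regression | logistic, for predictors of maturation | none stated |
| Repeated measures | GLM-RM (its two groups follow the M/N sentence, so most naturally M and N) | none stated |
| Outcome | maturation at three months, defined in 3.2 | events, none primary, no time point |
| Test for the outcome | stated | none stated |

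**2. Several events, none primary.** If the five named events were each tested at 0.05 and the tests were independent (assumed), the chance of at least one false positive is 1 − 0.95^5 = 0.226. Access events are probably correlated, so this is only a guide.

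**3. Baseline imbalance, no true effect.** Assume a prognostic factor present in 30% of intervention and 50% of control patients that multiplies risk by R. The apparent risk ratio is (0.7 + 0.3R)/(0.5 + 0.5R).

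- R = 2: 1.3/1.5 = 0.87 (1.15 if the imbalance is reversed).
- R = 3: 1.6/2.0 = 0.80 (1.25 if reversed).

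For a true risk ratio of 0.75:

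- R = 2: 0.75 × 0.867 = 0.65, or 0.75/0.867 = 0.87.
- R = 3: 0.75 × 0.80 = 0.60, or 0.75/0.80 = 0.94.

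**4. Chance of a falsely significant benefit.** This is the exact binomial probability, summed over all 2×2 tables with two-sided p < 0.05 and the lower rate in the intervention group. Assumed: 50 or 100 patients per group and control event rates of 10%, 20% or 33%. The range is borrowed from the background ("Estimates of non-maturation rates vary from 10% to 33% in AVF"); it is a non-maturation range, not an event rate for Aim 2.

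| Imbalance | Chi-square (uncorrected) | Fisher |
|---|---|---|
| none | about 2.5% | 1–2% |
| R = 2 | 4–10% | 1.5–7.5% |
| R = 3 | 5–18% | 2–14% |

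The rise is modest in most of these settings. The main harm is a biased estimate.

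**5. Unequal detection.** This applies only if a scan-dependent event is counted and controls are scanned less. Assume 90% of stenoses are found in the intervention group and a proportion d in controls. The observed ratio is 0.75 × 0.90/d.

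| d in controls | 0.30 | 0.50 | 0.70 | 0.80 | 0.90 |
|---|---|---|---|---|---|
| Observed ratio (true 0.75) | 2.25 | 1.35 | 0.96 | 0.84 | 0.75 |

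With equal scanning the bias is nil. At d = 0.70 the benefit nearly vanishes, and at d = 0.50 it is reversed.

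**The case against.** The strongest reply is that the plan says more than the one sentence suggests. Section 3.2 has a single list of access events, which is the obvious meaning of the outcome events in 3.3, and it is recorded in enrolled patients, which reads as both groups. The same section sorts enrolled patients with a functional AVF by their three-month ultrasound, so controls may have had scans too. The entry limits (age 18–70, radiocephalic fistula, no earlier vessel surgery on that arm) narrow the room for confounding. Every magnitude above is assumed.

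Most of this stands and limits the point. A reader might infer any of three stronger things:

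- *The outcome is wholly undefined.* The section 3.2 list is a natural referent. What is missing is a primary event and a time point.
- *Allocation is shown to be non-random.* It is unstated. The cohort label leans that way, but front matter is missing from the available text, so a statement there cannot be excluded.
- *Controls were not followed or not scanned.* The text is unclear on their schedule; it does not say this.

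The reply does not supply a test, an effect measure, a baseline comparison or an adjustment for this contrast. A chi-square test could be inferred from its use elsewhere in 3.3, but it would still be crude. Restrictive entry criteria reduce confounding without removing it.

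**Conclusion.** The concern holds in this limited form. As written, the plan leads to a crude comparison, over an open-ended event list that includes stenosis, between groups not shown to be randomised. Such a comparison cannot by itself support a claim that the follow-up protocol is beneficial.

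The size of the bias is unknown. The 0.60 to 0.94 range for a true ratio of 0.75 depends on the assumed 30% against 50% imbalance and a two- or threefold risk factor. The detection figures depend on two further conditions that the documents leave open: that a scan-dependent event is counted, and that controls are scanned less. The conclusion itself rests on what the text omits, not on these figures. Random allocation documented elsewhere would largely answer the confounding part. The unset primary event and the unclear control scans would remain.

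**What to change.** In section 3.3, for intervention against control:

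1. **Main outcome.** Choose one access event from the section 3.2 list that does not depend on scheduled ultrasound, for example AVF thrombosis, within six months of surgery. Record it in the same way in both groups, count early failures, and include everyone operated on. The exclusion of patients with "Predicted duration of MHD less than six months, such as transferring to peritoneal dialysis, planning to kidney transplantation, or short life expectancy" should keep early departures few. Report stenosis and scan-prompted operations separately and descriptively, and state which scans controls have.
2. **Analysis.** Collect the section 3.2 baseline data in both groups and tabulate them by group. Report the group effect with a 95% confidence interval, both crude and adjusted for a small set of baseline covariates fixed in advance (for example age and sex). Use a method suited to few events, such as penalised logistic regression, if needed.
3. **Allocation and wording.** State how patients were allocated. Unless it was random, report an association and not a test of benefit, because a few covariates cannot remove all confounding.

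The cost is SAP wording plus baseline and event recording in controls. The downside is fewer countable events and a wider interval than a pooled list of events would give.
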